#### **7.6.7 Diabetic Ketoacidosis-related Events**

The cumulative number of diabetic ketoacidosis-related events occurring from Days 75 to 365 inclusive after IAT will be summarized descriptively by treatment group and in total. The cumulative number of diabetic ketoacidosis-related events for a patient will be the number of events recorded on CRF Page 27.1. Treatment groups will be compared using a two-sided t-test or non-parametric Wilcoxon rank-sum test.

### **7.7 Exploratory Analysis**

The safety population will be used for the summarization and analysis of all exploratory data. Additional exploratory analyses beyond what is outlined below may be done.

#### **7.7.1 Inflammatory Chemokines/Cytokines**

Inflammatory chemokines/cytokines to be summarized include serum levels of CXCL8, CCL2 (MCP-1), CCL3, CCL4, CXCL10 (IP-10), CXCL9 (MIG), IL-6, IL-10, INF- $\gamma$ , TNF- $\alpha$ , and IL-1 $\beta$ . Values are collected as 2 basal samples at pre-infusion hospital admission (6 to 24 hours apart) and at 6, 12, 24, 72, 120, and 168 hours after IAT.

Observed values at each time point and baseline (the average of the two basal samples) and change from baseline (follow-up value minus baseline value) at each post-transplant time point will be summarized descriptively by treatment group and in total.

Observed values will also be presented as box plots for each treatment group at each time point in order to graphically examine the time course of each parameter for each treatment group.

The relationship between inflammatory chemokines/cytokines response (including AUC, peak level, and maximum change from baseline) and exposure to reparixin may be explored graphically, with inflammatory chemokines/cytokine response plotted against total reparixin dose (in mg/kg) received.

REP0112

Statistical Analysis Plan

- Area under the curve will be computed as follows. When parameter values are below the limit of detection, an appropriate value will be assumed in the calculation of area under the curve. Missing parameter values will be imputed via linear interpolation, and the average of the two basal samples (values, and mid-point of the sample times) will be used as the first sample in the computation of the AUC. Once these rules have been applied to the data, AUC for a parameter will be computed using the trapezoidal rule. For ease of interpretation, the AUC value obtained will be divided by the total time the scale is assessed for reporting purposes. Computation of AUC will be based on actual collection times, unless actual collection time is missing, in which case the scheduled collection time will be used.
- Peak level for any given inflammatory chemokine/cytokine parameter will be the maximum post-baseline value, where the baseline value will be the average of the two basal values.
- Maximum change from baseline for any given inflammatory chemokine/cytokine parameter will be the greatest change from baseline value, where change from baseline is computed as a post baseline value minus the baseline value and where baseline value is the average of the two basal values.

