#### 4.2.4. Exploratory endpoints

- Time course of inflammatory chemokines/cytokines as assessed by serum level of CXCL8, CCL2 (MCP-1), CCL3, CCL4, CXCL10 (IP-10), CXCL9 (MIG), IL-6, IL-10, INF-γ, TNF-α, and IL-1β [time frame: pre-infusion hospital admission (2 basal samples collected 6 to 24 hrs apart;

both samples will be obtained before surgery and before Investigational Product administration is started) and 6, 12, 24, 72, 120 and 168hrs after the end of islet infusion].

- Proportion of patients who are randomized but do not receive IAT [time frame: transplant day].
- Time course of serum microRNA-375 (miR-375) [time frame: pre-infusion hospital admission (sample will be obtained before surgery and before Investigational Product administration is started) and 6, 12, 24, 72, 120 and 168hrs after the end of islet infusion].

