## 2 DEFINITIONS AND DERIVED VARIABLES

Area Under the Curve (AUC), C-peptide: When C-peptide values are below the limit of detection (0.05 ng/mL), a value equal to the limit of detection will be assumed in the calculation of area under the curve. Missing C-peptide values will be imputed via linear interpolation, and the average of the two basal samples (values, and mid-point of sample times) will be used as the first sample in the computation of the AUC. Once these rules have been applied to the data, AUC for C-peptide will be computed using the trapezoidal rule. For ease of interpretation, the AUC value obtained will be divided by the total time the scale is assessed for reporting purposes. Computation of AUC will be based on actual collection times, unless actual collection time is missing, in which case the scheduled collection time will be used.

AUC0-72H, miR-375: Missing miR-375 values will be imputed via linear interpolation. Once these rules have been applied to the data, AUC0-72H for miR-375 will be computed using the trapezoidal rule. Computation of AUC0-72H will be based on actual collection times, unless actual collection time is missing, in which case the scheduled collection time will be used.

Other definitions and derived variables are found within the applicable subsections of Section 3, Statistical Methods.

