#### 3.3.1 Inflammatory Chemokines/Cytokines

Inflammatory chemokines/cytokines to be summarized include serum levels of CXCL8, CCL2 (MCP-1), CCL3, CCL4, CXCL10 (IP-10), CXCL9 (MIG), IL-6, IL-10, INF- $\gamma$ , TNF- $\alpha$ , and IL-1 $\beta$ . Values are collected as 2 basal samples at pre-infusion hospital admission (6 to 24 hours apart) and at 6, 12, 24, 72, 120, and 168 hours after IAT. Mean values for each inflammatory chemokine/cytokine will be plotted for each sample time point by treatment group.

AUC0-72H will be computed as defined in Section 7.7.1 of SAP version 2.0. AUC0-72H for CCL2, IL-6 and IL-10 will be plotted versus IEQ as a regression curve for each treatment group. The slope and intercept of the regression line and R^2 will be calculated and displayed on the figure. The p-value testing the slope for difference from zero will also be displayed.

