Figure 14.4.5.5	Area Under the Curve for C-peptide at Day 365 During First 4 Hours of a Mixed Meal Tolerance Test and Not Corrected for IEQ/kg Versus IEQ/kg – Only Patients Receiving IEQ/kg $\leq 5000$	Intent to Treat Population
Figure 14.4.5.6	Area Under the Curve for C-peptide at Day 365 During First 4 Hours of a Mixed Meal Tolerance Test and Not Corrected for IEQ/kg Versus IEQ/kg – Only Patients Receiving IEQ/kg $\leq 5000$	Per Protocol Population
Figure 14.4.11.1	Inflammatory Chemokines/ Cytokines, Plots of Mean Values Over Time	Safety Population
Figure 14.4.12.1	Area Under the Curve for CCL2, IL-6 and IL-10 During 72 Hours Following Transplant Versus IEQ, [Parameter Name]	Safety Population
Figure 14.4.15.1	miR-375, Plots of Mean Values over Time	Safety Population
Figure 14.4.15.2	Area Under the Curve for miR-375 During 72 Hours Following Transplant Versus IEQ	Safety Population

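### The exploratory cytokine AUC0-72H starts hours before transplant, so it spans at least 81 h and shifts with basal-draw timing; the miR-375 AUC has no stated start point

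*SAP*

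**What the plan says.** **Cytokine rule (SAP 7.7.1).** For the cytokine AUC, "the average of the two basal samples (values, and mid-point of the sample times) will be used as the first sample". On the clock, "Computation of AUC will be based on actual collection times, unless actual collection time is missing". On scaling, "the AUC value obtained will be divided by the total time the scale is assessed for reporting purposes". Nothing in that section cuts the curve at transplant or moves the basal value to transplant.

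**72-hour version (SAP Addendum 3.3.1).** AUC0-72H for CCL2, IL-6 and IL-10 "will be computed as defined in Section 7.7.1 of SAP version 2.0"; no different start point is given. Figure 14.4.12.1 is titled "Area Under the Curve for CCL2, IL-6 and IL-10 During 72 Hours Following Transplant Versus IEQ". It carries a regression line for each arm, with R² and a p-value for slope against zero.

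**Sampling (Protocol 4.2.4, 7.1.1, 7.1.5, Appendix 5).** The two basal cytokine samples are 6 to 24 h apart, and "both samples will be obtained before surgery and before Investigational Product administration is started". Study drug starts 6 to 18 h before islet infusion starts. Later samples are at 6, 12, 24, 72, 120 and 168 h after islet infusion ends. There is no sample at 0 h.

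**miR-375 (SAP Addendum 2).** This marker has its own rule: "Missing miR-375 values will be imputed via linear interpolation", followed by trapezoids on actual times. No first sample is named and there is no division by time. Figure 14.4.15.2 is titled "Area Under the Curve for miR-375 During 72 Hours Following Transplant Versus IEQ". Listing 16.2.15.1 shows two pre-transplant rows ahead of the 6-hour row, whereas Protocol Appendix 14.6.3 plans one basal miR-375 sample.

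**The concern.** SAP Section 5 has nearly the same basal rule for the C-peptide AUC in the mixed meal test. There the basal samples fall within 20 minutes before the meal, so their exact placement hardly matters. For cytokines the same rule reaches back many hours, by an amount that differs between patients. It then fills surgery, islet infusion and the first 6 h afterwards with one straight line.

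Two things follow. The quantity is not what its name and figure title say it is. And two patients with identical basal values and identical post-transplant courses get different AUCs because their basal blood was drawn at different times. That variation has nothing to do with islet mass or drug, and it enters regressions meant to relate the inflammatory response to islet mass.

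**Working it through.** The documents give no numerical result for this AUC, so there is no stated figure to reproduce.

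**Step 1: lead time from the protocol windows.** Suppose the second basal sample is drawn just before study drug starts. The mid-point of the pair then precedes the start of islet infusion by

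L = (drug start before infusion) + (gap between basal samples)/2.

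- Shortest: 6 + 6/2 = 9 h
- Wide end of both windows: 18 + 24/2 = 30 h

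The 30 h is not a cap. Protocol 7.1.1 lists basal sampling within a screening evaluation done up to 72 h before randomization, so the samples may be earlier. The duration of the islet infusion adds to L, because later samples are timed from its end.

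**Step 2: span of the AUC.** 72 + 9 = 81 h and 72 + 30 = 102 h.

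**Step 3: effect on the reported value.** Write b for the basal value, y6 for the 6-hour value, m = (b + y6)/2, and A for the trapezoidal AUC from 6 to 72 h. Then

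- raw AUC = A + m × (L + 6)
- time average = [A + m × (L + 6)] / (72 + L)

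The time average is a weighted mean of m and A/66. It rises with L if m is above A/66, falls if m is below, and does not move if they are equal. The profiles below are assumptions, not trial data.

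| Basal; 6/12/24/72 h | A | m | L = 9 h | L = 30 h | Change |
|---|---|---|---|---|---|
| 1; 10/6/3/1.5 | 210 | 5.5 | 292.5/81 = 3.611 | 408/102 = 4.000 | +10.8% |
| 5; 500/300/150/50 | 9,900 | 252.5 | 13,687.5/81 = 169.0 | 18,990/102 = 186.2 | +10.2% |
| 1; 50/25/8/2 | 663 | 25.5 | 1,045.5/81 = 12.907 | 1,581/102 = 15.500 | +20.1% |
| 1; 6/10/5/1.5 | 294 | 3.5 | 346.5/81 = 4.278 | 420/102 = 4.118 | −3.7% |
| 1; 3/6/10/3 | 435 | 2 | 465/81 = 5.741 | 507/102 = 4.971 | −13.4% |
| 1 throughout | 66 | 1 | 81/81 = 1 | 102/102 = 1 | 0% |

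The first three profiles have their maximum at 6 h, the next two at 12 h and 24 h.

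**Step 4: with the basal value at 0 h.** For the first profile the AUC is 210 + 5.5 × 6 = 243, or 243/72 = 3.375 as a time average, whatever the basal draw time.

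**Step 5: miR-375, only if its pre-transplant sample enters at its actual time.** With one basal sample the lead is at least 6 h, and 18 h if drawn just before a drug start at the early end of the window. The AUC is not time-averaged. On the first profile the raw AUC is 210 + 5.5 × 12 = 276 and 210 + 5.5 × 24 = 342, against 243 with the basal value at 0 h (+13.6% and +40.7%).

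**The case against.** The best counter-argument is that 0-72H already states the integration limits, and that SAP 7.7.1 supplies only handling rules. The curve would then be cut at 0 h. This helps but does not settle the matter. With no 0 h sample, the value at 0 h would still be read off a line whose slope depends on L. On the first profile that value is 1 + 9 × 9/15 = 6.4 at a 9 h lead and 1 + 9 × 30/36 = 8.5 at 30 h. The 0 to 72 h AUCs are then 210 + 6 × (6.4 + 10)/2 = 259.2 and 210 + 6 × (8.5 + 10)/2 = 265.5. The spread falls to 2.4% but does not vanish, and the text does not say that this reading is meant.

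Other points on that side stand:

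- A reader might infer that the line runs up to a 6-hour peak and so always inflates the AUC. No document says when any marker peaks, and the table shows that the sign depends on the profile.
- A reader might quote the much larger rise in the raw AUC (292.5 to 408 on the first profile, +39.5%). The cytokine AUC is reported as a time average, so that figure does not describe it.
- A reader might treat miR-375 as having the same defect. Its rule is separate and silent on the first sample; the listing is only suggestive.
- A reader might infer a biased drug comparison. No between-arm AUC test is planned, and randomization is double-blind and balanced within centres, so there is no evident reason for basal timing to differ by arm.
- The plot against reparixin dose (SAP Figure 14.4.12) claims neither 72 hours nor a post-transplant start. Because drug begins before islet infusion, a curve that starts earlier is defensible there.
- Observed values, change from baseline and peak level do not use the first trapezoid.

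**Conclusion.** The point holds for the cytokine AUC0-72H. As written, it includes a patient-specific pre-transplant interval of at least 9 h, which contradicts its name and figure title and makes it depend on basal-draw scheduling. Between 9 h and 30 h leads the time-averaged value moves by about 10% on two of the assumed profiles with a 6 h maximum and 20% on the third. It moves the other way, by about 4% to 13%, on the two with later maxima. These sizes rest on the assumed profiles and on the second basal sample being drawn just before study drug. The actual spread of leads is not in the documents.

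For miR-375 the finding is narrower: the start point is undefined, and the listing and the protocol disagree on the number of basal samples.

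The consequence is minor. It adds noise to exploratory regressions on islet mass. Primary and secondary endpoints are unaffected.

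**What to change.** In SAP Addendum 2 and 3.3.1:

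1. Define time 0 as the end of islet infusion.
2. Assign the basal value to time 0: the mean of the two samples for cytokines, the single planned sample for miR-375.
3. Integrate from 0 to 72 h using actual post-infusion times.
4. Where a time average is reported, divide by that 0 to 72 h span. State for each marker whether it is time-averaged.
5. Reconcile the two pre-transplant rows in Listing 16.2.15.1 with the one planned miR-375 sample.

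The cost is a few sentences and a programming change before database lock, with no new data. The small downside is the assumption that a pre-surgery value still holds at the end of islet infusion, after surgery and hours of study drug. A 6 to 72 h AUC, which uses no basal value, can be shown beside it as a check.

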#### 7.7.2 MicroRNA-375

MicroRNA-375 is collected pre-transplant and at 6, 12, 24, 72, 120, and 168 hours post-transplant.

Observed values at each time point and change from pre-transplant (follow-up value minus pre-transplant value) at each post-transplant time point will be summarized descriptively by treatment group and in total.

Observed values will also be presented as box plots for each treatment group at each time point in order to graphically examine the time course of MicroRNA-375 for each treatment group.

### 8 DATA MONITORING COMMITTEE

Safety and efficacy data will be reviewed on an ongoing basis by an independent DMC. Full details of the activities and responsibilities of the DMC are provided in the DMC Charter for the study.

The DMC will assess the safety and efficacy of the interventions during the trial and will monitor the overall conduct of the clinical trial. The DMC will provide recommendations to Dompé about stopping or continuing the trial. To contribute to enhancing the integrity of the trial, the DMC may also formulate recommendations to Dompé relating to the selection/recruitment/retention of participants, their management, improving adherence to protocol-specified regimens and retention of participants, and the procedures for data management and quality control.

The DMC:

- Will review unblinded data. To this purpose, an independent statistician not affiliated with the conduct of the trial will liaise with the CRO statistician and will have access to those components of the database necessary to generate the reports for the DMC.
- Will be responsible for the ongoing (at least every 4 months) review of safety data throughout the trial. Primary among the safety data that will be reviewed are serious adverse events. In particular, the DMC will monitor the number of deaths for both arms of the study to assess whether mortality is consistent with historical data. The DMC also will give attention to post-surgical reoperation and clinically significant coagulation abnormalities (intra-abdominal as well as gastrointestinal hemorrhage have been reported to be the most common reasons for reoperation).
- Will review efficacy data in an ongoing manner to enable the assessment of the acceptability of safety in the context of emerging evidence about efficacy, i.e. measures of metabolic control and graft function.

REP0112

*Statistical Analysis Plan*

- Will be advisory to Dompé and make recommendations to Dompé regarding the continuation of the trial and potential modifications to the design and conduct of the trial. These recommendations will be made in a manner to maintain confidentiality of emerging information about efficacy and safety, unless access to certain data is needed to enable Dompé to make decisions about the DMC recommendations. Dompé will be responsible for promptly reviewing the DMC recommendations, to decide whether to continue or terminate the trial, and to determine whether amendments to the protocol or changes in the study conduct are required

The independent statistician will use this SAP as a guideline for developing the outputs that are to be produced to facilitate DMC data review and deliberations.

## 9 INTERIM ANALYSES

Primary endpoint data will not be available until each patient reaches one year post randomization. Hence, it is expected that the majority of enrollment and treatment will be completed before meaningful evidence is available regarding treatment effect on the primary endpoint. Thus, traditional group sequential methods would have more limited utility in this setting.

The DMC will give careful consideration to the appropriateness of trial continuation if there is emerging evidence that reparixin is harmful. One component of this assessment will be the rate of unexpected deaths. Based on historical experiences from the published Minnesota series for 1977-2011 that includes 356 adults, 217 underwent pancreatectomy and IAT from 2006-2011. There was 1 unexpected death within 12 months of transplant. This translates to an estimated 0.5% rate.

The DMC will consider the following guidelines regarding early termination based on the occurrence of unexpected deaths. Early termination will be considered if:

- there are at least 2 unexpected deaths in the first 33 reparixin patients (an outcome with 1.2% chance if the true event rate is 0.5%);
- there are at least 3 unexpected deaths in reparixin patients at any time in the trial (an outcome with 0.2% chance in 50 reparixin patients if the true event rate is 0.5%).

In making any recommendations about termination, the totality of data will be considered, including the number of unexpected deaths in the control group, and the available evidence about efficacy and the overall safety profile.

The DMC will also give particular attention to clinically significant coagulation abnormalities, including but not limited to intra-abdominal or gastrointestinal hemorrhage. Early termination would be considered if the rate of clinically significant post-surgical complications that require reoperation reliably exceeds the rate expected currently in standard practice settings. Insights about that rate in standard practice settings will be provided by a literature review, and will include the publication for the Minnesota series, where intra-abdominal as well as gastrointestinal hemorrhage have been reported to be the most common reasons for reoperation (Sutherland, 2012).

The DMC will also consider early termination if the quality of conduct of the trial is such that the trial will not be able to provide a timely and reliable answer to the questions it was designed to address.

REP0112

Statistical Analysis Plan

**10 TABLES, FIGURES, AND LISTINGS FOR CLINICAL STUDY REPORT****Section 14.1, Disposition, Baseline Characteristics, and Exposure Tables**

Table 14.1.1	Patient Disposition	Screened Patients
Table 14.1.2	Patient Disposition by Site	Screened Patients
Table 14.1.3	Protocol Deviations	Intent to Treat Population
Table 14.1.4	Protocol Deviations by Site	Intent to Treat Population
Table 14.1.5.1	Demographics	Safety Population
Table 14.1.5.2	Demographics	Intent to Treat Population
Table 14.1.5.3	Demographics	Per Protocol Population
Table 14.1.6	Specific Clinical History	Safety Population
Table 14.1.7	Specific Clinical History by Site	Safety Population
Table 14.1.8	Significant Medical History	Safety Population
Table 14.1.9	Concomitant Medications	Safety Population
Table 14.1.10	Investigational Product Exposure	Safety Population

**Section 14.2, Efficacy Tables**

Table 14.2.1.1	Proportion of Insulin-independent Patients at Day 365 Following Islet Auto-Transplantation	Intent to Treat Population
Table 14.2.1.1.A	Proportion of Insulin-independent Patients at Day 365 Following Islet Auto-Transplantation	Intent to Treat Population Sensitivity Analysis
Table 14.2.1.1.B	Proportion of Insulin-independent Patients at Day 365 Following Islet Auto-Transplantation	Intent to Treat Population Sensitivity Analysis, Site 01 Only
Table 14.2.1.2	Proportion of Insulin-independent Patients at Day 365 Following Islet Auto-Transplantation	Per Protocol Population
Table 14.2.2.1	Analysis of Proportion of Insulin-independent Patients at Day 365 Following Islet Auto-Transplantation, Sensitivity Analysis	Intent to Treat Population
Table 14.2.2.1.A	Analysis of Proportion of Insulin-independent Patients at Day 365 Following Islet Auto-Transplantation, Sensitivity Analysis	Intent to Treat Population Sensitivity Analysis
Table 14.2.2.1.B	Analysis of Proportion of Insulin-independent Patients at Day 365 Following Islet Auto-Transplantation, Sensitivity Analysis	Intent to Treat Population Sensitivity Analysis, Site 01 Only
Table 14.2.2.2	Analysis of Proportion of Insulin-independent Patients at Day 365 Following Islet Auto-Transplantation, Sensitivity Analysis	Per Protocol Population
Table 14.2.3.1	Area Under the Curve for C-peptide During First 4 Hours of a Mixed Meal Tolerance Test	Intent to Treat Population
Table 14.2.3.2	Area Under the Curve for C-peptide During First 4 Hours of a Mixed Meal Tolerance Test	Per Protocol Population
Table 14.2.4.1	Average Daily Insulin Requirements	Intent to Treat Population
Table 14.2.4.2	Average Daily Insulin Requirements	Per Protocol Population
Table 14.2.5.1	Time Course of Glucose (unit) at Day 75	Intent to Treat Population
Table 14.2.5.2	Time Course of Glucose (unit) at Day 75	Per Protocol Population

REP0112

Statistical Analysis Plan

Table 14.2.6.1	Time Course of Glucose (unit) at Day 365	Intent to Treat Population
Table 14.2.6.2	Time Course of Glucose (unit) at Day 365	Per Protocol Population
Table 14.2.7.1	Time Course of C-peptide (unit) at Day 75	Intent to Treat Population
Table 14.2.7.2	Time Course of C-peptide (unit) at Day 75	Per Protocol Population
Table 14.2.8.1	Peak C-peptide (unit) on Day 75 and Time to Peak	Intent to Treat Population
Table 14.2.8.2	Peak C-peptide (unit) on Day 75 and Time to Peak	Per Protocol Population
Table 14.2.9.1	Time Course of C-peptide (unit) at Day 365	Intent to Treat Population
Table 14.2.9.2	Time Course of C-peptide (unit) at Day 365	Per Protocol Population
Table 14.2.10.1	Peak C-peptide (unit) on Day 365 and Time to Peak	Intent to Treat Population
Table 14.2.10.2	Peak C-peptide (unit) on Day 365 and Time to Peak	Per Protocol Population
Table 14.2.11.1	Time Course of Insulin (unit) at Day 75	Intent to Treat Population
Table 14.2.11.2	Time Course of Insulin (unit) at Day 75	Per Protocol Population
Table 14.2.12.1	Time Course of Insulin (unit) at Day 365	Intent to Treat Population
Table 14.2.12.2	Time Course of Insulin (unit) at Day 365	Per Protocol Population
Table 14.2.13.1	$\beta$ -score	Intent to Treat Population
Table 14.2.13.2	$\beta$ -score	Per Protocol Population
Table 14.2.14.1	Proportion of Patients With HbA1c $\leq$ 6.5% at Day 365	Intent to Treat Population
Table 14.2.14.2	Proportion of Patients With HbA1c $\leq$ 6.5% at Day 365	Per Protocol Population
Table 14.2.15.1	Cumulative Number of Severe Hypoglycemic Events	Intent to Treat Population
Table 14.2.15.2	Cumulative Number of Severe Hypoglycemic Events	Per Protocol Population
Table 14.2.16.1	Proportion of Patients With HbA1c $\leq$ 6.5% at Day 365 and Free of Severe Hypoglycemic Events From Day 75 to 365 Inclusive	Intent to Treat Population
Table 14.2.16.2	Proportion of Patients With HbA1c $\leq$ 6.5% at Day 365 and Free of Severe Hypoglycemic Events From Day 75 to 365 Inclusive	Per Protocol Population

